5.0 DOSE MODIFICATIONS FOR TOXICITIES

In addition to dose modifications, this section provides information regarding management of toxicities known to be associated with protocol therapy.

In the sections below, when protocol therapy is to be discontinued, in general all protocol therapy should be discontinued and the patient would be taken off protocol therapy. However, if a patient requires permanent discontinuation of isotretinoin, the patient may continue on protocol therapy and receive the other therapy components (e.g., irinotecan, temozolomide, dinutuximab, GM-CSF).

5.1 Dose Modifications for Hematologic Toxicity

Patients must meet hematologic criteria for study entry and at the start of each treatment cycle.

5.1.1 Neutropenia

Patients who experience neutropenia that causes a delay of ≥ 14 days between treatment cycles in the absence of other toxicity requiring dose modification should have the temozolomide dose reduced by 25% for subsequent cycles (see dose reduction nomogram in [Appendix IX](#)). If patient experiences neutropenia that causes a delay of ≥ 14 days between treatment cycles despite this dose reduction, protocol therapy must be discontinued and patient must be removed from protocol therapy.

5.1.2 Thrombocytopenia

For patients who experience thrombocytopenia that causes a delay of ≥ 14 days between treatment cycles with or without other hematologic toxicities, the dose of temozolomide should be reduced by 25% for subsequent cycles (see dose reduction nomogram in [Appendix IX](#)). If patient experiences thrombocytopenia that causes a delay of ≥ 14 days between treatment cycles despite this dose reduction, protocol therapy must be discontinued.

5.1.3 Delayed Recovery of Platelets and Neutrophils

Patients who do not meet criteria to start the next treatment cycle (see [Section 4.5.1](#) or [Section 4.6.1](#)) within 28 days after the planned subsequent cycle start date (i.e. there is a ≥ 4 week delay in start of next cycle) must be removed from protocol therapy.

5.2 Dose Modifications for Non-hematologic Toxicity

Patients who have experienced non-hematologic toxicity should receive subsequent doses of study medications as described in the following sections. [Section 4.5.1](#) and [Section 4.6.1](#) describe criteria to be met prior to starting subsequent cycles.

5.2.1 Dose Modifications for Diarrhea

See [Appendix V](#) for patient/family instructions for supportive care measures for patients who develop therapy-associated diarrhea. Also included are specific instructions for loperamide dosing.

- If Grade 4 therapy-associated diarrhea is experienced by a patient with no evidence of infectious etiology and despite maximal use of anti-diarrheal medications ([Appendix V](#)) and appropriate use of prophylactic antibiotics

([Section 4.2.1](#)), the dose of irinotecan should be reduced by 25% for subsequent cycles (i.e., irinotecan dose 37.5 mg/m²/dose for patients with BSA ≥ 0.6 m²).

- If Grade 4 therapy-associated diarrhea recurs without an infectious etiology despite reducing the dose of irinotecan by 25%, the dinutuximab dose should also be decreased by 25% for subsequent cycles (i.e. dinutuximab dose 13 mg/m²/day).
- If Grade 4 diarrhea recurs despite maximal use of anti-diarrheals, prophylactic antibiotics, and these dose reductions, the patient must come off protocol therapy.

5.2.2 Dose Modifications for Nausea and Vomiting

- For patients with Grade 4 regimen-related nausea and vomiting and for patients with Grade 3 regimen-related nausea and vomiting > 7 days in duration who did not receive appropriate anti-emetic therapy, adjustments in the anti-emetic regimen should be made during the next cycle of therapy.
- If severe (Grade 4 or Grade 3 > 7 days) regimen-related nausea and vomiting recurs despite optimized anti-emetic usage, doses of irinotecan and temozolomide should both be reduced by 25% for subsequent cycles (i.e. irinotecan dose 37.5 mg/m²/dose; for temozolomide see dose reduction nomogram in [Appendix IX](#)).
- If severe regimen-related nausea and vomiting recurs despite the dose reduction, the patient must come off protocol therapy.

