Special precautions: Temozolomide capsules are available in 6 different strengths. Daily doses are usually comprised of multiple capsules of different strengths. To prevent errors, each strength of temozolomide capsules must be dispensed in a separate bottle and the total number of each strength of capsules needed for the full course must be dispensed at one time. See hyperlink to the drug monograph provided in [Section 6.0](#) for additional details and examples.

Irinotecan: IV over 90 minutes daily

Days: 1-5

Dose: For BSA $\geq 0.6 \text{ m}^2$, the dose of irinotecan is 50 mg/m²/dose.

For BSA $< 0.6 \text{ m}^2$, please see the table below. The dose of irinotecan in the table is expressed as final dose in **mg** to be administered.

IRINOTECAN Dosing If BSA < 0.6 m²	
BSA (m ²)	Dose
0.25-0.29	8 mg
0.3-0.34	12 mg
0.35-0.39	15 mg
0.4-0.44	18 mg
0.45-0.49	22 mg
0.5-0.54	24 mg
0.55-0.59	28 mg

Note: Irinotecan should be administered at least 1 hour after enteral temozolomide has been given.

Higher incidence of cholinergic symptoms has been reported with more rapid infusion rates.

See the Parenteral Chemotherapy Administration Guidelines (CAG) for special precautions, suggestions for patient monitoring, and hydration on the COG website at:

https://www.cogmembers.org/_files/disc/Pharmacy/ChemoAdminGuidelines.pdf

Dinutuximab: IV over 10 hours* daily

Days: 2-5

Dose: 17.5 mg/m²/dose

Note: Due to the increased risk of capillary leak and respiratory compromise with dinutuximab administration, patients should not have dyspnea at rest or an oxygen requirement when starting the first dose of dinutuximab. **Before starting dinutuximab**, please obtain a copy of management recommendations for anaphylaxis and hypotension available in [Appendix XI](#). It is recommended that these be available on the inpatient unit to facilitate treatment decisions should these symptoms occur.

Refer to [Section 4.4.3](#) for premedication and supportive care for the prevention of anticipated toxicities associated with dinutuximab, and for monitoring during the dinutuximab infusion. Additional information can be found in [Appendix XI](#).

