5.2.3 Dose Modifications for Dehydration

- If dehydration is related to diarrhea or nausea/vomiting, the guidance in [Section 5.2.1](#) or [Section 5.2.2](#) should be followed.
- If regimen-related \geq Grade 3 dehydration persists for > 3 days in the absence of significant diarrhea or nausea/vomiting, doses of irinotecan and temozolomide should both be reduced by 25% for subsequent cycles (i.e. irinotecan dose is 37.5 mg/m² for patients with BSA ≥ 0.6 m²; for temozolomide see dose reduction nomogram in [Appendix IX](#)).
- If \geq Grade 3 regimen-related dehydration recurs and persists for > 3 days despite the dose reduction, the patient must come off protocol therapy.

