5.2.9 Other Non-Hematologic Toxicities

The above sections cover dose modifications for most anticipated adverse events with this regimen. For Grade 3 or higher non-hematologic toxicities not specified above or for non-hematologic toxicities not specified above that prolong the start of subsequent cycles by ≥ 14 days, the doses of both irinotecan and temozolomide should be reduced by 25% in the subsequent cycle. If Grade 3 or higher non-hematologic toxicity recurs or cycles are again delayed by ≥ 14 days, the patient should be removed from protocol therapy.

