APPENDIX IX: TEMOZOLOMIDE REDUCED (75 MG/M²) DOSING NOMOGRAMS

For patients with BSA < 0.6 m² who require a dose reduction, use the table below.

The dose of temozolomide in the table is expressed as final dose in **mg** to be administered.

TEMOZOLOMIDE Dose Reduction If BSA < 0.6 m²	
BSA (m ²)	Dose
0.25-0.29	10 mg
0.30-0.34	15 mg
0.35-0.39	20 mg
0.40-0.44	25 mg
0.45-0.49	30 mg
0.50-0.54	35 mg
0.55-0.59	40 mg

Use the nomogram below for patients whose BSA is at least 0.6 m² receiving capsule formulation.

Example: For a patient with a BSA of 0.66 m², the calculated dose = 49.5 mg/dose; administered dose per nomogram = 50 mg temozolomide/dose.

BSA (m ²)	Calculated daily dose (mg)	Administered daily dose (mg)
0.6-0.63	43-47	45
0.64-0.70	48-52	50
0.71-0.76	53-57	55
0.77-0.83	58-62	60
0.84-0.90	63-67	65
0.91-0.96	68-72	70
0.97-1.03	73-77	75
1.04-1.10	78-82	80
1.11-1.16	83-87	85
1.17-1.23	88-92	90
1.24-1.30	93-97	95
1.31-1.36	98-102	100
1.37-1.43	103-107	105
1.44-1.50	108-112	110
1.51-1.56	113-117	115
1.57-1.63	118-122	120
1.64-1.70	123-127	125
1.71-1.76	128-132	130
1.77-1.83	133-137	135
1.84-1.90	138-142	140
1.91-1.96	143-147	145
≥ 1.97	148	150

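### Section 5.2.2 gives the 25% irinotecan reduction as 37.5 mg/m² for every patient; below a BSA of 0.6 m² that figure is almost always too small a cut, and in the smallest children it exceeds the full dose

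*Combined protocol and SAP*

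**What the plan says.** Section 5.2.2 of the protocol applies when severe regimen-related nausea and vomiting (Grade 4, or Grade 3 for more than 7 days) comes back despite optimized anti-emetics. It orders that "doses of irinotecan and temozolomide should both be reduced by 25% for subsequent cycles", and a parenthesis spells out what that means: "irinotecan dose 37.5 mg/m²/dose; for temozolomide see dose reduction nomogram in" Appendix IX. The irinotecan figure carries no body-size limit.

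The neighbouring rules are worded differently:

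- Section 5.2.1 (diarrhea): "irinotecan dose 37.5 mg/m²/dose for patients with BSA ≥ 0.6 m²".
- Section 5.2.3 (dehydration): "irinotecan dose is 37.5 mg/m² for patients with BSA" of at least 0.6 m².
- Section 5.2.9 (other non-hematologic toxicity): "the doses of both irinotecan and temozolomide should be reduced by 25% in the subsequent cycle", with no mg/m² figure at all.

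The full irinotecan dose is set in Sections 4.4.7 and 4.5.7. At BSA of 0.6 m² or more it is 50 mg/m². Below that a seven-band table applies, and "The dose of irinotecan in the table is expressed as final dose in" mg. For temozolomide, Appendix IX covers the small patients separately: "For patients with BSA < 0.6 m² who require a dose reduction, use the table below".

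**The concern.** Section 5.2.2 presents 37.5 mg/m² as the meaning of a 25% reduction. That holds only where the starting dose is 50 mg/m². Below 0.6 m² the starting dose is a fixed amount that works out at 27.6 to 50.9 mg/m², so one sentence gives two different doses for the same child.

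Nothing else in the protocol supplies the right number. Temozolomide and isotretinoin both have reduced-dose tables below 0.6 m² (Appendix IX and Section 5.2.7); irinotecan has none. The only reduced irinotecan figure a site finds in Section 5.2.2 is 37.5 mg/m².

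This is a dose in a toxicity rule. A site that uses it would cut irinotecan by too little, or raise it in the smallest children, after severe vomiting has already recurred. Section 5.2.3 also routes vomiting-related dehydration to this rule. If vomiting recurs after the reduction, the patient must leave protocol therapy, and under Section 9.3.1 leaving before five cycles are complete counts against feasibility. No effect on that endpoint has been quantified, and any effect is likely small.

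**Working it through.** **Inputs.** Full dose at BSA ≥ 0.6 m²: 50 mg/m². Full dose below 0.6 m², by band: 8, 12, 15, 18, 22, 24 and 28 mg (Sections 4.4.7 and 4.5.7, identical tables). Ordered cut: 25%. Stated reduced dose: 37.5 mg/m² (Section 5.2.2).

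**Step 1: reproduce the stated figure.** 0.75 × 50 = 37.5 mg/m². This is correct for BSA ≥ 0.6 m².

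**Step 2: express the small-patient full dose per m².** Full dose ÷ BSA is lowest at 8 ÷ 0.29 = 27.6 mg/m² and highest at 28 ÷ 0.55 = 50.9 mg/m². It equals 50 only at 28 ÷ 0.56.

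**Step 3: compare the stated figure with the ordered cut.** For each BSA from 0.25 to 0.59 m² in steps of 0.01 (35 values):

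- stated dose = 37.5 × BSA
- intended dose = 0.75 × table dose
- share of full dose = 37.5 × BSA ÷ table dose, which should be 75%

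| BSA (m²) | Full dose (mg) | Intended, 75% (mg) | 37.5 × BSA (mg) | Share of full dose | Against intended dose |
|---|---|---|---|---|---|
| 0.25-0.29 | 8 | 6 | 9.375-10.875 | 117-136% | +56 to +81% |
| 0.30-0.34 | 12 | 9 | 11.25-12.75 | 94-106% | +25 to +42% |
| 0.35-0.39 | 15 | 11.25 | 13.125-14.625 | 88-98% | +17 to +30% |
| 0.40-0.44 | 18 | 13.5 | 15.0-16.5 | 83-92% | +11 to +22% |
| 0.45-0.49 | 22 | 16.5 | 16.875-18.375 | 77-84% | +2 to +11% |
| 0.50-0.54 | 24 | 18 | 18.75-20.25 | 78-84% | +4 to +13% |
| 0.55-0.59 | 28 | 21 | 20.625-22.125 | 74-79% | -2 to +5% |

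Worked example at 0.25 m²: 37.5 × 0.25 = 9.375 mg; 9.375 ÷ 8 = 117% of the full dose; 9.375 ÷ 6 = 1.56, or 56% above the intended dose.

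**Step 4: counts over the 35 values.**

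- Less than a 25% cut (share above 75%): 33, all but 0.55 (73.7%) and 0.56 m² (75.0%).
- Exactly a 25% cut: 1 (0.56 m²).
- Within 5 percentage points of a 25% cut: 9.
- Equal to the full dose: 1 (0.32 m²).
- Above the full dose: 7 (0.25 to 0.29, 0.33 and 0.34 m²).

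**Step 5: check the other half of the cut.** Temozolomide below 0.6 m², Appendix IX over the full table: 10/15, 15/20, 20/30, 25/35, 30/40, 35/50 and 40/55, which is 67, 75, 67, 71, 75, 70 and 73% of full dose. The temozolomide reduction is therefore not affected.

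**The case against.** The strongest reply is that the governing order, a 25% cut, is correct and the parenthesis only illustrates it. The calculation 0.75 × 50 is right; what is missing is a phrase of scope. A site treating a child below 0.6 m² works from a fixed-milligram table and never has a 50 mg/m² dose to convert, and the sections on either side state the limit. This stands as a reason why many sites would get it right. It does not make the text right, because the parenthesis is worded as an equivalence and contradicts the percentage beside it.

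Second, the most striking cases are the least likely. A material rise above full dose occurs only at 0.25-0.29 m²; at 0.33-0.34 m² the excess is about 3-6%. Every patient has completed Induction and tandem transplant and enrolls at least 56 days after the last stem cell infusion, so these sizes may be rare. The protocol nevertheless tabulates doses down to 0.25 m² and does not say how many such patients it expects.

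Third, the count of 33 of 35 weights each 0.01 m² equally and includes near misses such as 76.3% at 0.57 m². At 13 of the 35 values the share is within 8 points of 75%, and Appendix IX itself tolerates departures of up to 8 points for temozolomide. That is fair, and the real gap lies mainly below 0.45 m². But the Appendix IX departures are towards a larger cut, whereas these are almost all towards a smaller one.

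Finally, harm needs a small child, recurrent severe vomiting and a site that follows the figure over the percentage, in a study analysing 40 patients. No probability can be put on that from the protocol, which limits how heavily the point should weigh.

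**Conclusion.** The concern holds. As written, Section 5.2.2 states a reduced irinotecan dose that disagrees with its own 25% instruction at 34 of the 35 BSA values below 0.6 m² and errs towards too much drug at 33 of them. The excess over the intended dose is 56-81% at 0.25-0.29 m², 11-22% at 0.40-0.44 m², and between -2% and +5% at 0.55-0.59 m².

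The conclusion assumes that the percentage is the intended rule, which Sections 5.2.1, 5.2.3 and 5.2.9 support, and that BSA is taken to two decimals as in the dosing tables. The practical effect depends on how many patients are below 0.6 m² and on whether a site follows the figure, neither of which the protocol gives. The text should be corrected because it is a dosing figure in a safety rule. Sample size, error rates and power are unaffected.

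**What to change.** In Section 5.2.2, limit the figure: irinotecan 37.5 mg/m²/dose for patients with BSA ≥ 0.6 m²; for BSA < 0.6 m², 75% of the table dose in Section 4.5.7. Before rounding, that is 6, 9, 11.25, 13.5, 16.5, 18 and 21 mg for the seven bands.

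Three of those values are not whole milligrams, so the amendment should also say how to round. A short reduced-dose irinotecan table below 0.6 m², like the one for temozolomide in Appendix IX, would settle the rounding and serve Sections 5.2.1, 5.2.3 and 5.2.9 as well. It is optional.

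The cost is one qualifying phrase in the next amendment, with no change to accrual, sample size or analysis.

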5.2.3 Dose Modifications for Dehydration

- If dehydration is related to diarrhea or nausea/vomiting, the guidance in [Section 5.2.1](#) or [Section 5.2.2](#) should be followed.
- If regimen-related \geq Grade 3 dehydration persists for > 3 days in the absence of significant diarrhea or nausea/vomiting, doses of irinotecan and temozolomide should both be reduced by 25% for subsequent cycles (i.e. irinotecan dose is 37.5 mg/m² for patients with BSA ≥ 0.6 m²; for temozolomide see dose reduction nomogram in [Appendix IX](#)).
- If \geq Grade 3 regimen-related dehydration recurs and persists for > 3 days despite the dose reduction, the patient must come off protocol therapy.

5.2.4 Dose Modifications for Elevations in ALT, AST, or GGT

- If elevations in ALT, AST or GGT occur such that values are > 20x ULN for any duration of time OR > 10x ULN but < 20x ULN and persisting for > 7 days, the dose of dinutuximab should be reduced by 25% for subsequent cycles (i.e. dinutuximab dose 13 mg/m²/day). For the purposes of this trial the ULN for ALT is defined as 45 U/L; institutional ULN values for AST and GGT should be used.
- If elevations of this magnitude involving same liver enzyme(s) recur despite the first dose reduction in dinutuximab, the dose of temozolomide should be reduced by 25% for subsequent cycles (i.e. for temozolomide see dose reduction nomogram in [Appendix IX](#)). If the dose limiting elevations of the same liver enzyme(s) recur despite the temozolomide dose reduction, the patient must come off protocol therapy.
- An elevation in ALT that causes a delay of ≥ 14 days between treatment cycles will also require a 25% reduction in the dose of dinutuximab for all subsequent

cycles (i.e. dinutuximab dose 13 mg/m²/day). If a delay of ≥ 14 days between treatment cycles recurs due to elevation in ALT despite the dose reduction, the patient should come off protocol therapy.

- For hepatic function parameters to begin isotretinoin during each cycle, please refer to treatment guidelines (Cycle 1 see [Section 4.4.2](#); Cycles 2-5 see [Section 4.5.2](#); Cycle 6 see [Section 4.6.1](#)). Refer to [Section 5.2.7](#) for isotretinoin-specific dose modifications if hepatic function abnormalities are attributed to isotretinoin.

5.2.5 Dinutuximab Specific Dose Modifications and Toxicity Management Recommendations

5.2.5.1 Treatment of dinutuximab-induced **severe hypotension** (without evidence of allergic reaction)

- a. If hypotension is severe and accompanied by poor perfusion, end organ dysfunction, or acidemia – Pediatric Advanced Life Support (PALS) guidelines should be followed and dinutuximab infusion should be discontinued.
- b. Treatment of **moderate hypotension** (without poor perfusion, end organ dysfunction or acidemia):
 - i. Immediately hold dinutuximab
 - ii. Give normal saline bolus (20 mL/kg as rapidly as possible)
 - iii. Stop or adjust doses of narcotics and sedating H1 blockers
 - iv. Consider use of Trendelenberg position

If hypotension persists after the above measures have been taken:

- v. Reassess perfusion and end organ function
- vi. Follow PALS algorithm if indicated
- vii. Repeat NS bolus OR
- viii. Consider use of albumin if albumin < 3 gm/dL
- ix. Consider use of PRBCs if Hb < 8 gm/dL
- x. Consider use of platelets if count < 50,000/ μ L
- xi. Consider transfer to the intensive care setting

If hypotension persists following 2 volume boluses, give an additional bolus and prepare to administer pressors: epinephrine or norepinephrine is preferred over dopamine, if possible

Note: Moderate Hypotension is defined as:

- i. Symptomatic decreases in blood pressure (BP) and/or
- ii. Systolic BP < 5th percentile based on age and height and baseline BPs OR
- iii. Systolic or diastolic BP decreased by > 20% below baseline

- c. Resumption of dinutuximab
 - i. For patients whose hypotension resolves promptly and completely with limited volume resuscitation (≤ 40 mL/kg) and without requirement for pressor support, dinutuximab may be restarted at 50% of the previous infusion rate.

Restart on the same day within 20 hours of the start of the day's infusion, if possible. If blood pressures are stable for 2 hours, the infusion may be given at full rate for the remainder of that day and subsequent days. If the patient again experiences hypotension requiring multiple volume boluses (e.g., > 40 mL/kg) when dinutuximab is given at full rate, but the patient tolerates the 50% infusion rate, then the remaining dinutuximab dose for that day and subsequent days should be given at 50% rate of the initial infusion rate. Do not continue an infusion for >20 hours. If the patient's hypotension has resolved, a newly formulated dose should be started on the calendar day following the day on which the patient experienced the hypotensive reaction, with the dose given at 50% of the initial infusion rate.

- If blood pressures are stable for 2 hours after resumption of dinutuximab at the reduced rate, the remainder of the antibody infusion may be given at the full rate.
 - If hypotension recurs at the reduced rate, the measures above should again be taken and no further dinutuximab should be given that day. The antibody infusion may be restarted the following day after ensuring that the patient is volume replete. The antibody rate upon resumption of treatment should be 50% of the initial rate. If blood pressures are stable for 2 hours, the infusion may be given at full rate for that day and subsequent days. If the patient's blood pressures are only stable at the 50% rate and not at full rate, then the remaining dinutuximab dose for that day and doses on subsequent days should be given at 50% of the initial infusion rate.
- ii. For patients who require multiple volume boluses for hemodynamic stabilization, dinutuximab should be resumed the following day at 50% of the initial infusion rate.
- If blood pressures are stable for 2 hours after resumption of dinutuximab at the reduced rate, the remainder of the antibody infusion may be given at the full rate.
 - If hypotension recurs at the reduced rate, the measures above should again be taken and no further dinutuximab should be given that day. The antibody infusion may be restarted the following day after ensuring that the patient is volume replete. The antibody rate upon resumption of treatment should be 50% of the initial rate. If blood pressures are stable for 2 hours, the infusion may be given at full rate for that day and subsequent days. If the patient's blood pressures are only stable at the 50% rate and not at full rate, the

remaining days' doses of dinutuximab should be given at the 50% rate of infusion.

- iii. For patients who require pressors for treatment of hypotension, if blood pressure is stable off pressors for at least 6 hours, administration of dinutuximab may be resumed at 50% of the initial infusion rate on the day following the hypotensive episode. Care should be taken to ensure that the patient is volume replete. Dinutuximab should not be given to patients who continue to require pressor support. Patients who require pressor support for ≥ 24 hours due to treatment-related hypotension despite appropriate volume resuscitation should discontinue protocol therapy. Patients who again require pressor support when dinutuximab is resumed must discontinue protocol therapy.

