Prior to dinutuximab administration (morning start recommended), administer IV bolus of normal saline (10-20 mL/kg) over 60-90 minutes. Bolus should be given concurrently with irinotecan infusion. On Day 2-5, start dinutuximab immediately following the completion of normal saline bolus and irinotecan infusion. Dinutuximab dose should start at 0.88 mg/m²/hour x 0.5 hour, then gradually increase to 1.75 mg/m²/hour for the remainder of the dose, if tolerated.

*The infusion duration may be extended up to 20 hours for anticipated toxicities (hypotension, tachypnea, etc.), not responding to other supportive measures, and the duration used should be recorded. **In the setting of dose reductions described in [Section 5.0](#), the infusion time must be no longer than 20 hours from initiation of dinutuximab, even if the full dose of dinutuximab antibody has not been delivered in that timeframe. Antibody administration should not be given beyond the specified schedule regardless of whether doses were modified or held per guidelines in [Section 5.0](#). The total dose given in 20 hours should be recorded.**

Sargramostim: Subcutaneous injection (preferred) or IV over 2 hours daily

Days: 6 through 12

Dose: 250 micrograms/m²/dose

Start sargramostim on Day 6 any time after the completion of Day 5 dinutuximab.

The standard route of administration is subcutaneous; in extenuating circumstances, IV administration over 2 hours is permitted. The reason for IV administration of this agent must be documented.

Sargramostim dose will be held if the total white cell count is > 50,000/ μ L. This is not a toxicity of sargramostim but rather a possible outcome related to its use. The sargramostim will be held until the total white cell count is less than 20,000/ μ L.

and then sargramostim will be resumed at 50% dose for the remainder of that cycle. Full dose sargramostim will be used for subsequent sargramostim cycles.

ISOTretinoin: PO BID

Days: 8-21 See additional starting criteria for ISOT in Section 4.4.2.

Dose: For $BSA \geq 0.6 \text{ m}^2$, the dose of ISOTretinoin is 80 mg/m²/dose BID, rounded to nearest 10 mg to accommodate capsule strength.

For $BSA < 0.6 \text{ m}^2$, please see table below. The dose of ISOTretinoin in the table is expressed as final dose in **mg** to be administered.

NOTE: dose BID. For example, if $BSA \geq 0.6 \text{ m}^2$, administer 80 mg/m²/dose BID. The total daily dose is 160 mg/m²/day.

ISOTretinoin Dosing If $BSA < 0.6 \text{ m}^2$	

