5.2.5.2 Treatment of allergic reactions/infusion reactions

- a. Mild allergic reactions/infusion reactions to dinutuximab infusion
 - i. A mild allergic reaction is limited to rash, flushing, urticaria, mild dyspnea – Grade 1 or 2
 - ii. The following recommendations do NOT apply to Grade 3 or 4 allergic reactions, including anaphylaxis
 - iii. Management
 - Decrease rate of dinutuximab to 50% of full rate
 - Perform serial exams at bedside
 - Administer H1 blocker (diphenhydramine, cetirizine recommended)
 - Administer H2 blocker
 - When symptoms resolve, resume original infusion rate
 - If symptoms recur when original rate is resumed, decrease to 50% rate again
 - Infusion must be stopped after 20 hours (whether the full dose of dinutuximab has been administered or not); document total amount of drug given in the 20 hour time period.
- b. Moderate to severe allergic reactions/infusion reactions to dinutuximab infusion
 - i. Moderate to severe reactions include any of the following: symptomatic bronchospasm, allergy-related edema/angioedema, hypotension, or anaphylaxis – Grade 3 or 4
 - ii. The following recommendations do NOT apply to Grade 1 or 2 allergic reactions
 - iii. Management
 - **Immediately hold dinutuximab**
 - Assess airway, breathing and circulation
 - Follow institutional guidelines for rapid response team notification if clinically indicated
 - For airway concerns

- Administer oxygen and albuterol immediately for bronchospasm
- Administer IV diphenhydramine
- Administer epinephrine (1:1000 IM recommended) immediately if upper airway involved or if airway issues are accompanied by cardiovascular collapse
- Administer IV hydrocortisone (1-2 mg/kg) if the patient has frank anaphylaxis with cardiorespiratory collapse OR if ≥ 2 doses of epinephrine are required OR if moderate to severe symptoms recur upon rechallenge with dinutuximab
- For hypotension in the setting of allergic reaction
 - Give normal saline bolus (20 mL/kg as rapidly as possible)
 - Stop or adjust doses of narcotics and sedating H1 blockers
 - Consider use of Trendelenberg position
 - See previous section for management of persistent hypotension

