5.2.5.4 Management of renal insufficiency (unrelated to hypotension)

- Consider the possibility of renal hypoperfusion in the context of borderline hypotension; administer volume if appropriate.
- If the patient's creatinine is elevated to ≥ 2 x the upper limit of normal for age/gender (see table in [Section 3.2.6.2](#)) and elevation persists despite optimized fluid management, hold dinutuximab.
- Modify dosing of concomitant medications that may contribute to or be affected by renal insufficiency.
- When urine output returns to normal and creatinine returns to < 2 x upper limit of normal for age/gender, resume dinutuximab at 50% rate. If renal function normalizes by the following day, dinutuximab may be administered at full rate. If renal function is not sufficiently improved (urine output normal and creatinine < 2 x ULN for age/gender) by Day 7, no further dinutuximab should be given during that cycle of therapy. If renal function has normalized by the planned start date for the next cycle, retreatment with dinutuximab is permitted.

5.2.5.5 Management of hyponatremia (\geq Grade 3; Na < 130 mEq/L and symptomatic or 120-124 mEq/L regardless of symptoms)

- Change hypotonic fluids to isotonic fluids as compatibilities permit
- Avoid administration of oral free water
- Correct fluid losses due to diarrhea
- 3% saline is only indicated in the following settings:
 - hyponatremia leading to seizure
 - drop in sodium level > 10 points in 6 hours or less
 - sodium level < 117 mEq/L
- If Grade 4 hyponatremia persists despite optimal fluid management, discontinue dinutuximab for the remainder of the cycle. Sodium should be monitored closely during the next cycle of therapy. If hyponatremia improves to Grade 2 or better, or baseline, empiric dose reduction is not required at the start of the next cycle of therapy, though dinutuximab would again be discontinued if Grade 4 hyponatremia were to persist despite optimal fluid management. In such cases, patient must discontinue protocol therapy.

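### The Day 7 limit for resuming dinutuximab after a renal hold conflicts with the Days 2-5 schedule, and the rate to which each 50% reduction refers is not defined

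*Combined protocol and SAP*

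**What the plan says.** **Schedule and rate.** Section 4.1 places dinutuximab on Days 2-5 and sargramostim on Days 6-12. Section 4.4.7, repeated in 4.5.7, gives "Dose: 17.5 mg/m²/dose" and "Dinutuximab: IV over 10 hours* daily", with this ramp: "Dinutuximab dose should start at 0.88 mg/m²/hour x 0.5 hour, then gradually increase to 1.75 mg/m²/hour". Each infusion ends 20 hours after it starts, whether or not the dose is complete, and the amount given is recorded. The same section adds: "Antibody administration should not be given beyond the specified schedule regardless of whether doses were modified or held per guidelines in" Section 5.0. Sargramostim starts on Day 6, after the Day 5 antibody.

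**Day limit after a renal hold.** Section 5.2.5.4 resumes dinutuximab once urine output and creatinine recover. If they have not recovered "by Day 7, no further dinutuximab should be given during that cycle of therapy".

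**Base of the 50% rate.**
- 5.2.5.1 c.i (hypotension, same-day restart): "dinutuximab may be restarted at 50% of the previous infusion rate".
- 5.2.5.1 c.i (hypotension recurs at full rate): doses for the rest of that day and "subsequent days should be given at 50% rate of the initial infusion rate". Parts c.ii and c.iii also refer to the initial rate.
- 5.2.5.2 a (mild allergic reaction): "Decrease rate of dinutuximab to 50% of full rate".
- 5.2.5.2 b (moderate to severe reaction): half of the previous rate.
- 5.2.5.3 (capillary leak) and 5.2.5.4 (renal): a 50% rate with no base.
- Appendix XI (bedside reference): half rate with no base.

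**The concern.** On the day limit, a site that follows 5.2.5.4 could give antibody on Day 6 or 7, and a site that follows 4.4.7/4.5.7 could not. Antibody on those days would overlap sargramostim. In Cycle 1 it would also fall within the Day 5-8 window for the post-dinutuximab sample.

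On the rate, 4.4.7 supplies two figures that could be called initial: the 0.88 mg/m²/h start and the 1.75 mg/m²/h running rate. Because of the 20-hour stop, a patient who stays at a low enough rate does not receive the whole dose. Previous and initial both occur within the hypotension pathway, so one patient can meet both words.

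What is at stake is how much antibody is delivered and on which days, and so what a completed cycle represents. Section 9.3.1 counts completed cycles without progression within 30 weeks. It sets no minimum antibody dose, and it does not count dose modifications against feasibility.

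**Working it through.** **Inputs.** From 4.4.7: dose 17.5 mg/m² per day, starting rate 0.88 mg/m²/h for 0.5 h, running rate 1.75 mg/m²/h, limit 20 h. From 4.1: Days 2-5, so four doses per cycle.

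**Plan's own figure: an infusion of about 10 hours.**
- Without the ramp: 17.5 / 1.75 = 10.0 h.
- With the ramp, assuming an immediate step to 1.75 after half an hour: 0.5 + (17.5 − 0.88 × 0.5) / 1.75 = 0.5 + 17.06 / 1.75 = 10.25 h. This agrees with the stated duration to within 2.5%.

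**A whole infusion at the reduced rate.** Delivered amount = rate × 20 h, capped at 17.5 mg/m².

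| Base of the 50% | Rate (mg/m²/h) | Delivered in 20 h | Share of dose |
|---|---|---|---|
| Running (full) rate, 1.75 | 0.875 | 17.5 mg/m² | 100% |
| Starting rate, 0.88 | 0.44 | 8.8 mg/m² | 50.3% |

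The ratio is 17.5 / 8.8 = 1.99.

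**One cycle.** Assume a reaction 2 h into the Day 2 infusion, a 1-h hold, and the reduced rate from then on.
- Given before the reaction: 0.44 + 1.5 × 1.75 = 3.065 mg/m². Time left: 20 − 3 = 17 h.
- Half of running rate: 3.065 + 17 × 0.875 = 17.94, capped at 17.5. With Days 3-5 the cycle total is 4 × 17.5 = 70.0 mg/m².
- Half of starting rate: 3.065 + 17 × 0.44 = 10.545. With Days 3-5 the total is 10.545 + 3 × 8.8 = 36.9 mg/m².

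On the day of the reaction, with the same 1-h hold, the ratio depends on timing: 1.94 for a reaction at 0.5 h, 1.66 at 2 h, 1.21 at 5 h and 1.00 at 8 h.

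**Same patient, full rate restored after two stable hours** (as 5.2.5.1 allows).
- Half of running rate: (17.5 − 3.065 − 1.75) / 1.75 = 7.25 h more, so the infusion ends at 5 + 7.25 = 12.25 h.
- Half of starting rate: (17.5 − 3.065 − 0.88) / 1.75 = 7.75 h more, so it ends at 12.75 h.

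Both end well inside 20 h with the whole dose given, so there is no difference.

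**Day limit.** Assume one dose per day, Day 7 as the last antibody day under 5.2.5.4, doses given on Days 2 and 3, a hold from Day 4 and recovery on Day 6.
- 5.2.5.4: up to two more doses (Days 6 and 7), four in all.
- 4.1 with 4.4.7/4.5.7: no more doses, two in all.

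**Next-day restart in 5.2.5.1 c.i.** One sentence allows full rate on later days after two stable hours. A later one starts a new dose the next calendar day at half of the initial rate if hypotension has resolved. The text does not say whether the second sentence is only for patients who were not restarted on the same day.

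**The case against.** The strongest case is that the wording is loose but the meaning is recoverable. Section 5.2.5.1 works with only two rates, full and 50%. The sentence ordering half of the initial rate concerns a patient who has just tolerated the 50% rate and failed full rate, so initial plausibly means the full rate before the reaction. A parallel bullet under c.ii uses a plain 50% rate. Half of the starting rate would be a quarter of full rate, which no passage mentions. These are fair points about the text, and they make the literal reading the less natural one. They do not make initial a defined term.

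A reader might infer that antibody exposure differs two-fold for the same patient after any hold. The documents do not support that. The ratio of 1.99 is a ceiling for a whole day at the reduced rate. It needs initial to mean 0.88 (or previous to mean it, for a reaction in the first half hour) and a patient who does not return to full rate. The full-rate wording in 5.2.5.2 a is a slow-down for a mild reaction, not a restart after a hold. The Day 7 text is for renal insufficiency alone. The next-day sentences in 5.2.5.1 c.i can be read as branches, because same-day restart is asked for only where possible.

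On days, one can argue that the specified schedule is undefined and follows the 20-hour limit, or that the 72-hour allowance in Section 4.0 covers Days 6-7. The first is true, although Days 2-5 is the natural meaning. The second does not settle the matter, because that allowance excludes whatever the protocol explicitly prohibits.

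**Conclusion.** The point holds in two limited parts.

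1. **Day limit, renal insufficiency only.** Section 5.2.5.4 contradicts 4.1 and 4.4.7/4.5.7, if the specified schedule means Days 2-5. In the example the difference is up to two infusions versus none.
2. **Rate base.** The reference for the 50% rate is inconsistent and undefined. The delivered dose is the same if initial means the pre-reaction full rate, or if full rate resumes after two stable hours. Under the literal starting-rate reading, with no return to full rate, the patient receives at most 8.8 instead of 17.5 mg/m² over a whole infusion. The cycle total is about 37 versus 70 mg/m² for a Day 2 reaction at 2 hours, with the assumed 1-hour hold and the reduced rate throughout.

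A reader might also infer that the feasibility result itself is distorted. Section 9.3.1 does not support that: the count does not move directly. What is affected is the exposure behind a completed cycle and how it can be interpreted. The documents do not say how many patients would be involved.

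**What to change.** Amend the wording in three places:
- Reconcile 5.2.5.4 with 4.1 and 4.4.7/4.5.7 so that the last permitted antibody day is the same in all of them, and define the specified schedule.
- Use one defined reference rate, in mg/m²/h, wherever a 50% or half rate is ordered: 5.2.5.1 to 5.2.5.4, including the moderate-to-severe allergic reaction text, and Appendix XI.
- State in 5.2.5.1 c.i which patients the next-calendar-day restart sentence covers.

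The study team decides which rate and which day are right. The cost is a text amendment and notice to sites. No new data are needed, because 4.4.7/4.5.7 already have sites record the extended infusion duration and the total dose given in 20 hours.
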